4.3. Withdrawal Criteria and Procedures for the Patient

In accordance with the Declaration of Helsinki (in accordance with the applicable country's acceptance), patients may voluntarily withdraw from the study at any time. The investigator also has the right to withdraw a patient from the study in the event of intercurrent illness, adverse events, pregnancy (Section 7.2), or other reasons concerning the health or well-being of the patient or in the event of lack of cooperation.

Each patient is free to withdraw from the study at any time, without prejudice to his/her continued care. A patient must be withdrawn from the study if any of the following events occur:

1. Patient withdraws consent or requests discontinuation from the study for any reason.
2. Patient develops an illness that would interfere with his/her continued participation.
3. Patient is noncompliant with the study procedures and assessments or administration of IMPs in the opinion of the investigator.
4. Patient takes prohibited concomitant medications as defined in this protocol.
5. A female patient has a confirmation of pregnancy during the study from a positive pregnancy test.
6. The sponsor requests withdrawal of the patient.
7. Patient experiences an adverse event or other medical condition, which indicates to the investigator that continued participation is not in the best interest of the patient.

Should a patient decide to withdraw from the study after administration of study drug or should the investigator decide to withdraw the patient, all efforts will be made to complete and report all observations up to the time of withdrawal. A complete final evaluation at the time of the patient's withdrawal should be made, and an explanation should be given as to why the patient is withdrawing or being withdrawn from the study.

The reason for and date of withdrawal from the study must be recorded on the source documentation and transcribed onto the CRF. If a patient withdraws consent, every attempt will be made to determine the reason. If the reason for withdrawal is an adverse event or a potentially clinically significant abnormal laboratory test result, monitoring will be continued until the event has resolved or stabilized, until the patient is referred to the care of a healthcare professional, or until a determination of a cause unrelated to the study drug or study procedure is made. The specific event or test result must be recorded on the source documentation and transcribed onto the CRF.

If a patient is found to have a positive ADA status after at least 2 doses of study drug in this OL study, the patient may be scheduled to complete an EOT visit. This testing would be done to enhance early data collection on potential washout samples.

All protocol-specific evaluations should be performed at the early withdrawal visit ([Table 1](#)). Patients who withdraw from the study will be asked to participate in a follow-up telephone assessment 12 weeks \pm 14 days after the early withdrawal visit. All protocol-specified evaluations should be performed during the follow up telephone assessment 12 weeks \pm 14 days after the early withdrawal visit ([Table 1](#)).

Patients should be treated with standard-of-care treatment after withdrawal from or withdrawal of the study, as appropriate.

For patients who are lost to follow-up (ie, patients whose status is unclear because they fail to appear for study visits without stating an intention to withdraw), the investigator should make every effort to re-establish contact with patient; attempts to contact the patient should be documented in the source documents. A patient should only be designated as lost to follow-up if the study center is unable to establish contact with the patient after 3 documented attempts via 2 different methods (ie, phone, text, e-mail, certified letter, etc).

See [Appendix F](#) for information regarding how the study will define and address patients who were lost to follow-up to help limit the amount and impact of missing data.

4.4. Replacement of Patients

A patient who is enrolled but does not complete the treatment period will not be replaced with another eligible patient.

4.5. Rescreening

Patients who did not rollover seamlessly from Study 30025 or 30027 may be considered for rescreening if they are excluded from study participation for required treatment for an asthma exacerbation within 4 weeks of screening or during the screening. A patient may be rescreened for this reason 1 time only. The duration between the first visit during the screening period and the rescreening must be >30 days.

There will be no rescreening of patients who do not meet the other entry criteria for this OL extension study.

4.6. Screening Failure

Screening failures are defined as participants who consent to participate in the clinical study but are not subsequently enrolled in the study. Minimum information to be collected includes, but is not limited to, demography, screening failure details, eligibility criteria, and any serious adverse events.

5. TREATMENTS

5.1. Investigational Medicinal Products Used in the Study

5.1.1. Test Investigational Medicinal Product

Reslizumab will be provided as a sterile solution in a pre-filled syringe (PFS) containing 110 mg (1.0 mL) reslizumab per syringe, formulated at 110 mg/mL in [REDACTED] sodium acetate, with [REDACTED] sucrose, [REDACTED] polysorbate 80, and pH 5.5 buffer (Table 2). Reslizumab will be provided as a clear to slightly hazy solution.

Study drug will be administered as sc injections in the thigh, abdomen, or upper arm(s) once every 4 weeks for a total of 9 doses.

The PFS has a staked 27G 0.5-inch needle. Injections of sc study drug can be given at a 90-degree angle or at a 45-degree angle. The injection can be given at a 90-degree angle if 2 inches of skin can be grasped between the thumb and the first finger. If only 1 inch of skin can be grasped, the injection should be administered at a 45-degree angle. The sites where injections are given should be at least 1 inch away from each other. Product should be removed from the refrigerator and allowed to equilibrate at room temperature for 15 to 30 minutes before administration. Administration will be conducted by qualified study personnel.

Additional information regarding the study drug can be found in the Pharmacy Manual.

Table 2: Investigational Medicinal Products Used in the Study

IMP name	Reslizumab
Trade name and INN, if applicable, or company-assigned number	CINQAIR® CINQAERO® Reslizumab
Formulation	Sterile solution containing 110 mg (1.0 mL) reslizumab per syringe and formulated at 110 mg/mL in [REDACTED] sodium acetate, with [REDACTED] sucrose, [REDACTED] polysorbate 80, and pH 5.5 buffer
Unit dose strength(s)/dosage level(s)	110 mg (1.0 mL) reslizumab per PFS
Route of administration	Subcutaneous injection Performed by qualified study personnel
Dosing instructions	Every 4 weeks
Packaging	PFSs to study centers
Manufacturer	Teva Pharmaceuticals

IMP=investigational medicinal product; INN=International Nonproprietary Name; PFS=pre-filled syringe.

Additional details may also be found in the current version of the IB for reslizumab. Product complaints procedures are described in [Appendix S](#).

5.1.1.1. Starting Dose and Dose Levels

The starting dose and maximal dose administered will be 110 mg/mL sc every 4 weeks.

5.2. Preparation, Handling, Labeling, Storage, and Accountability for IMPs**5.2.1. Storage and Security**

The investigator or designee must confirm that appropriate temperature conditions have been maintained for all IMPs received and that any discrepancies are reported and resolved before use of the IMPs.

Reslizumab must be stored in a refrigerator at controlled temperature (2°C to 8°C), must not be frozen, and must be protected from light. Reslizumab will be kept in a secure area (eg, locked refrigerator). The study center should have a process for monitoring the storage temperature of unused study drug.

5.2.2. Labeling

Supplies of IMPs will be labeled according to the current International Council for Harmonisation (ICH) guidelines on Good Clinical Practice (GCP) and Good Manufacturing Practice (GMP) and will include any locally required statements. If necessary, labels will be translated into the local language.

5.2.3. Accountability

Each IMP shipment will include a packing slip listing the contents of the shipment, return instructions, and any applicable forms.

The investigator is responsible for ensuring that deliveries of IMPs and other study materials from the sponsor are correctly received, recorded, handled, and stored safely and properly in accordance with the Code of Federal Regulations (CFR) or national and local regulations and used in accordance with this protocol.

Only patients enrolled in the study may receive IMPs, and only authorized staff at the investigational center may supply the IMP.

All IMPs must be stored in a secure, environmentally controlled, and monitored (manual or automated) area in accordance with the labeled storage conditions or appropriate instructions with access limited to the investigator and authorized staff at the investigational center.

The investigator, institution, or the head of the medical institution (where applicable) is responsible for IMP accountability, reconciliation, and record maintenance (ie, receipt, reconciliation, and final disposition records).

A record of IMP accountability (ie, IMP and other study materials received, used, retained, returned, or destroyed) must be prepared and signed by the principal investigator or designee, with an account given for any discrepancies. Empty, partially used, and unused IMP will be disposed of or returned to the sponsor or designee.

5.3. Justification for Investigational Medicinal Products

5.3.1. Justification for Dose of Test Investigational Medicinal Product

The platform of evidence that supports the range of the reslizumab dose response is based on the observed effects on lung function and other clinical endpoints in patients with eosinophilic asthma (Studies P00290 [0.3- and 1.0-mg/kg doses], Res-5-0010 [3.0-mg/kg dose], and 3081 [0.3- and 3.0-mg/kg doses]), on eosinophil depletion in the blood in healthy subjects (Study 1102 [0.3-, 1.0-, 2.0-, and 3.0-mg/kg doses]), and in the blood and affected tissue in patients with asthma (Studies I96-350, 3081, and P00290) and eosinophilic esophagitis (Study Res-5-0002 [1.0-, 2.0-, and 3.0-mg/kg doses]). Refer to the IB for a summary and comprehensive presentation of these data. Briefly, treatment with iv reslizumab at a dose of 0.3 mg/kg produced substantially smaller and less durable reductions in the number of blood or tissue eosinophils (ie, sputum) than doses \geq 1 mg/kg. In contrast, the magnitude of reductions in blood or tissue eosinophils at doses \geq 1 mg/kg (ie, 1, 2, or 3 mg/kg) was similar. Improvements in patients in the reslizumab 0.3-mg/kg treatment group for FEV₁ were 0.129 L at week 16 (p=0.0481), but other efficacy endpoint results were more variable (eg, no treatment effect on forced vital capacity [FVC] and forced expiratory flow at 25% and 75% of the FVC [FEF_{25%-75%}] was observed for patients in the reslizumab 0.3-mg/kg treatment group). Therefore, iv doses of \geq 1 mg/kg are anticipated to be clinically effective in most patients. Based on these clinical and eosinophil PD data, Teva has chosen reslizumab 110 mg administered once every 4 weeks as the fixed dose to study in the sc program. This approximates a 1-mg/kg iv dose for the average patient (ie, 70 kg) when adjusted to account for sc bioavailability (ie, 67%). Modeling and simulation demonstrate that the steady-state trough serum concentrations of reslizumab after administration of the proposed 110-mg sc dosing regimen are expected to fall within the range of exposures that produced meaningful effects on both blood eosinophils and FEV₁ in patients with eosinophilic asthma. Therefore, a fixed dose of 110 mg sc once every 4 weeks is anticipated to provide sufficient efficacy.

5.4. Treatment After the End of the Study

Patients will return to the care of their primary physician and/or asthma specialist after the end of this study.

5.5. Restrictions

Medications prohibited before and/or during the study are described in Section 5.6. Restrictions in regard to sexual activity and required laboratory values are provided in the inclusion and exclusion criteria.

5.6. Prior and Concomitant Medication or Therapy

Any prior or concomitant therapy, medication (including corticosteroids), or procedure a patient has had at screening up to the end of the study period, including follow-up, will be recorded on the appropriate CRF. Generic or trade name, indication, and dosage will be recorded. The sponsor will encode all therapy and medication according to the World Health Organization (WHO) drug dictionary.

At each clinic visit after the screening visit, the investigator will ask patients whether they have taken any medications (other than study drug), including over-the-counter medications, vitamins, or herbal or nutritional supplements, since the previous visit. Indication, dosage, and start and end dates should be entered on the appropriate CRF.

For patients on maintenance OCS treatment, patients should be evaluated at each patient interaction (study visit) and their OCS dose reduced as clinically appropriate. Maintenance prednisone will not be provided by the sponsor. In an effort to standardize a patient's maintenance therapy, it is encouraged that the investigators prescribe prednisone/prednisolone as the maintenance corticosteroid preparation if deemed necessary.

With the exception maintenance OCSs for the treatment of asthma, any systemic immunosuppressive or immunomodulatory biologic (eg, anti-immunoglobulin E mAb or other mAb [eg, mepolizumab, benralizumab, dupilumab] or soluble receptors) or non-biologic (eg, methotrexate or cyclosporine) will be prohibited during this study.

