- j. The patient is currently using any systemic immunosuppressive or immunomodulatory biologic (eg, anti-immunoglobulin E mAb or other mAb [eg, mepolizumab, benralizumab, dupilumab] or soluble receptors) or non-biologic (eg, methotrexate or cyclosporine), except maintenance oral corticosteroids, for the treatment of asthma (up to and including 40 mg of prednisone daily or equivalent every-other-day dosing). Note: Previous use of such agents that occurred >5 half-lives from the initial screening visit may be allowed.

- k. The patient participated in a clinical study other than approved Teva reslizumab studies within 30 days or 5 half-lives of the investigational drug before screening, whichever is longer.
- l. The patient has a history of an immunodeficiency disorder, including human immunodeficiency virus (HIV).
- m. The patient has current or suspected drug and/or alcohol abuse.
- n. The patient has an active helminthic parasitic infection or was treated for one within 6 months of screening.
- o. The patient has a history of allergic reaction or hypersensitivity to any component of the study drug.
- p. The patient is expected to be poorly compliant with study procedures or visits.
- q. The patient is a vulnerable patient (eg, a patient who is or may be for any reason unable to take care of him or herself, unable to protect him or herself against significant harm or exploitation, or kept in detention).

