6. ASSESSMENT OF EFFICACY

6.1. Assessments of Efficacy

6.1.1. Asthma Exacerbations

A CAE is defined as a clinically judged deterioration in asthma control, as determined by the investigator and as evidenced by new or worsening asthma signs or symptoms based on the patient history, handheld eDiary/spirometry device, physical examination, and/or ambulatory or clinic visit assessment of lung function, and that results in a medical intervention, including at least one of the following:

- use of systemic corticosteroids (oral or injection) or at least a doubling from a stable maintenance oral corticosteroid dose for at least 3 days
- asthma-specific hospital admission
- asthma-specific emergency department visit

Additional medication and/or medical intervention that would satisfy the CAE definition occurring within 7 days of the last day of a prior CAE event will be considered as part of the same event for analysis purposes.

All asthma exacerbations (mild/moderate/severe) should be recorded on the asthma exacerbation CRF. The information on the CRF will be used to determine if an asthma exacerbation meets CAE criteria.

The CAE start and stop dates will be collected in order to determine the exacerbation duration. The start date of a CAE will be the start date of the initial medical intervention (eg, use of systemic corticosteroids [oral or injection] or at least a doubling from a stable maintenance oral corticosteroid dose for at least 3 days, asthma-specific hospital admission, or asthma-specific emergency department visit, whichever comes first). The stop date is the last day of systemic corticosteroids or the last day of an asthma-specific hospitalization or emergency department visit, whichever is later. For patients who are on a stable maintenance oral corticosteroid dose and receive at least a doubling of that dose for 3 days, the stop date is when they return to their baseline dose. For patients receiving a new use of oral corticosteroid or at least a doubling from their stable maintenance oral corticosteroid dose for at least 3 days that did not return to baseline, the CAE stop date will be the day when they have been on a stable dose for at least 10 days.

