7.1.7. Withdrawal Due to an Adverse Event

Any patient who will experience an adverse event may be withdrawn from the study at any time at the discretion of the investigator. If a patient is withdrawn wholly or in part because of an adverse event, both the adverse events page and the termination page of the CRF will be completed at that time.

The patient will be monitored at the discretion of the investigator (eg, until the event has resolved or stabilized, until the patient is referred to the care of a healthcare professional, or until a determination of a cause unrelated to the study drug or study procedure is made). The investigator must inform the medical monitor as soon as possible of all patients who are being considered for withdrawal due to adverse events. Additional reports must be provided when requested.

If a patient is withdrawn from the study for multiple reasons that include adverse events, the termination page of the CRF should indicate that the withdrawal was related to an adverse event. An exception to this requirement will be the occurrence of an adverse event that, in the opinion of the investigator, is not severe enough to warrant discontinuation but requires the use of a prohibited medication, thereby requiring discontinuation of the patient. In such a case, the reason for discontinuation would be the need to take a prohibited medication, not the adverse event.

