APPENDIX C. QUALITY CONTROL AND QUALITY ASSURANCE

Protocol Amendments and Protocol Deviations and Violations

Protocol Amendments

No changes from the final approved (signed) protocol will be initiated without the prior written approval or favorable opinion of a written amendment by the independent ethics committee/institutional review board (IEC/IRB) and national and local competent authorities, as applicable, except when necessary to address immediate safety concerns to the patients or when the change involves only nonsubstantial logistics or administration. The Principal Investigator at each investigational center, the coordinating investigator (if applicable), and the sponsor will sign the protocol amendment.

Protocol Violations

Any deviation from the protocol that affects, to a significant degree, (a) the safety, physical, or mental integrity of the patients in the study and/or (b) the scientific value of the study will be considered a protocol violation. Protocol violations may include non-adherence on the part of the patient, the investigator, or the sponsor to protocol-specific inclusion and exclusion criteria, primary objective variable criteria, or Good Clinical Practice (GCP) guidelines; noncompliance to investigational medicinal product (IMP) administration; use of prohibited medications.

Protocol violations will be identified and recorded by investigational center personnel in the case report form (CRF). All protocol violations will be reported to the responsible IEC/IRB, as required.

When a protocol violation is reported, the sponsor will determine whether to discontinue the patient from the study or permit the patient to continue in the study, with documented approval from the medical expert. The decision will be based on ensuring the safety of the patient and preserving the integrity of the study.

Changes in the inclusion and exclusion criteria of the protocol are **not** prospectively granted by the sponsor. If investigational center personnel learn that a patient who did not meet protocol inclusion and exclusion criteria was entered in a study, they must immediately inform the sponsor of the protocol violation. If such patient has already completed the study or has withdrawn early, no action will be taken but the violation will be recorded.

Information to Study Personnel

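### Protocol Section 5.6 does not expressly exempt steroid courses given for an exacerbation from the prohibited-medication rule; read literally with Sections 4.3 and 7.1.7, this conflicts with the exacerbation endpoint

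*Protocol*

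**What the plan says.** **The prohibition.** Protocol Section 5.6 opens its ban with "With the exception maintenance OCSs for the treatment of asthma, any systemic immunosuppressive or immunomodulatory biologic" and, after a list of biologic examples, closes it with "or non-biologic (eg, methotrexate or cyclosporine) will be prohibited during this study". Exclusion criterion j in Section 4.2 is built the same way: it bars current use of the same class, "except maintenance oral corticosteroids, for the treatment of asthma (up to and including 40 mg of prednisone daily" or an every-other-day equivalent.

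**The consequence, mandatory version.** Section 4.3 states: "A patient must be withdrawn from the study if any of the following events occur". Item 4 of the list that follows is "Patient takes prohibited concomitant medications as defined in this protocol". Section 7.1.7 agrees, describing an adverse event that "requires the use of a prohibited medication, thereby requiring discontinuation of the patient".

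**The consequence, discretionary version.** Section 5.7 leaves withdrawal for noncompliance to the investigator and the sponsor. Appendix C counts use of prohibited medication among possible protocol violations, and after a reported violation "the sponsor will determine whether to discontinue the patient from the study or permit the patient to continue in the study".

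**The endpoint.** Section 6.1.1, repeated in SAP 6.3.1.1, lists as its first qualifying CAE intervention "use of systemic corticosteroids (oral or injection) or at least a doubling from a stable maintenance oral corticosteroid dose for at least 3 days". Hospital admission or an emergency department visit for asthma also qualifies. Interventions within 7 days of the end of a CAE are merged with it, and a course that does not return to baseline ends only once the dose has been stable for at least 10 days.

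**The concern.** An exemption for maintenance OCS is needed only if corticosteroids belong to the banned class. If they do, a new oral course or a steroid injection for an exacerbation is left inside the ban, and Section 4.3 item 4 then requires withdrawal. Yet the same treatment is what makes many exacerbations countable, and the merging and stop-date rules make sense only if the patient is still observed afterwards.

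Under that reading, withdrawal depends on the outcome:

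- **CAE frequency.** Repeat events would be missed in the patients most likely to have them.
- **Later efficacy summaries.** Protocol Section 9.3 uses observed data only, so week-24 and week-36 FEV1, ACQ-6, AQLQ12+ and OCS values would lean toward patients without steroid-treated CAEs.
- **Long-term safety.** Exposure, the purpose of the study, would be lost in less stable patients.
- **Disposition and violation tables.** With about 140 centers, sites that read the text differently would put two policies into SAP 5.2 and 5.9.

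**Working it through.** The plan states no figure on this point, and the study is descriptive with a sample size not based on power. The main check is textual; the arithmetic only illustrates scale.

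**Step 1. Is an exacerbation course inside the ban?** The structure of Section 5.6 and exclusion j suggests that it is. No passage names corticosteroids as prohibited, and the non-biologic examples are methotrexate and cyclosporine. No passage exempts exacerbation courses either. The text therefore permits the literal reading without stating it.

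**Step 2. What follows from a prohibited drug?** Sections 4.3 and 7.1.7 say withdrawal. Section 5.7 and Appendix C say case-by-case decision. These disagree for any prohibited drug, whatever the answer to step 1.

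**Step 3. Does the SAP settle it?** The SAP says that it prevails where the two documents differ. It contains no prohibited-medication rule and repeats the CAE definition unchanged, so it does not.

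**Step 4. What would the literal reading do to the CAE count?** The first CAE is still counted at its start date. For a patient who stops early, SAP 6.3.1.2 counts events to the last dose plus 4 weeks and lists all events. The count is truncated after that point.

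**Step 5. How many patients? (illustration)**

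Inputs: 360 planned patients (Protocol 9.1); a 36-week treatment period (Protocol 3.1); 24% systemic corticosteroid use on intravenous reslizumab 3.0 mg/kg (Protocol 1.3.1). The documents give no CAE rate for the subcutaneous product, so the rates below are assumptions.

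*From the 24% figure:*

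- Applied directly: 0.24 × 360 = 86.4, about 86 patients.
- Treated as a 52-week figure and scaled at constant hazard: 1 − 0.76^(36/52) = 0.173, and 0.173 × 360 = 62.3, about 62 patients.

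*From assumed rates of steroid-treated CAEs*, with P(at least one) = 1 − exp(−rate × 36/52):

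| Rate per patient-year | P(at least one in 36 weeks) | Of 360 |
|---|---|---|
| 0.3 | 18.8% | 68 |
| 0.5 | 29.3% | 105 |
| 1.0 | 50.0% | 180 |
| 1.5 | 64.6% | 233 |

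The 24% comes from another route and dose and from studies of 16 to 52 weeks, and it may include maintenance use. The rate-based figures assume one common rate and full 36-week follow-up; variation between patients would lower them.

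**The case against.** The strongest reply is that the protocol plainly expects steroid treatment of exacerbations, and that the specific section should guide the general one. Section 6.1.1 sets out dates and merging rules for these courses. Section 5.6 itself asks for corticosteroids to be recorded, without limiting this to maintenance use, and its carve-out can be read as a clarification for avoidance of doubt. Exclusion h handles recent exacerbation treatment separately from exclusion j and only for non-seamless patients, which suggests two different subjects. Many sites would probably read the ban narrowly.

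Much of this stands. A reader might infer that the protocol forbids steroid courses for exacerbations and forces withdrawal. The documents do not support that as a flat statement: the ban on such courses is an inference from the carve-out, and Section 5.7 and Appendix C leave room to continue.

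It does not remove the point. The narrow reading is also an inference, since nobody wrote the exemption down. Exclusions h and j overlap only in part, one covering the previous 4 weeks and the other current use, so h does not settle what j or Section 5.6 covers. And the mismatch between mandatory and discretionary withdrawal remains on either reading.

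**Conclusion.** The point holds as a drafting inconsistency with consequences for the analysis. Section 5.6 lacks an express position on exacerbation courses, its literal reading conflicts with Section 6.1.1 and SAP 6.3.1, and the documents give two different consequences for prohibited medication.

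A reader might go further and infer that CAE frequency would be capped at about one per patient, or that later FEV1, questionnaire and OCS values would come only from exacerbation-free patients. Neither follows. A CAE can qualify through admission or an emergency visit without steroids. A doubled maintenance dose is arguably still maintenance OCS and so exempt. Events count to the last dose plus 4 weeks. SAP 4.4 also maps an early-termination assessment to the next scheduled visit when 3 to 5 weeks have passed since the last dose. Truncation and a lean toward more stable patients are the supportable descriptions.

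The illustrated size is about 62 to 86 of 360 patients from the intravenous program's 24%, or 105 to 180 at an assumed 0.5 to 1.0 steroid-treated CAE per patient-year. Both depend on the literal reading being applied, and neither is an estimate for this study. Confidence that the passages need reconciling is good; how sites would read them cannot be known from the documents.

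**What to change.** Reconcile Protocol Sections 4.3, 5.6, 5.7, 6.1.1, 7.1.7 and Appendix C, so that one explicit statement says (a) whether systemic corticosteroid courses given for a CAE fall inside the prohibition, and (b) whether withdrawal for prohibited medication is mandatory or discretionary. Which answer is clinically right is for the sponsor; none is proposed here. Exclusion j should be checked for consistency with the result.

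The cost is about one sentence plus aligned wording in the other sections, by clarification letter or amendment.

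Optionally, SAP 5.2 and 5.9 could each carry one row for withdrawals or violations triggered only by corticosteroid treatment of a CAE. Those tables already report withdrawals by reason and violations by category, so the rows are not essential once the wording is reconciled.
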